Official Title: Examining the Impact of Stress on the Emotionally Reinforcing Properties of Alcohol in Heavy Social Drinkers: A Multimodal Investigation Integrating Laboratory and Ambulatory Methods

NCT number: NCT03449095

Document Date: 4/24/2024

Study Protocol

Participants in this study will be male and female social drinkers, age 21-30. To be eligible, all participants will need to identify at least one eligible same-gender friend. Participants will be excluded from participation if they have a history of adverse reaction to the amount of beverage employed in the study, if they have a history of alcohol treatment or of major problems associated with alcohol, or if they are especially light drinkers or abstainers. Participants must also report comfort with the dose of alcohol administered in the study. Individuals will be excluded if they have medical conditions that contraindicate alcohol administration, if they are illiterate, or if they are non-fluent English speakers. Participants must not be dependent on any substance other than nicotine or caffeine, and must not qualify for severe Alcohol Use Disorder, as assessed at the time of study screening via DSM-V. Females who are pregnant or trying to conceive will be excluded.

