The laboratory portion of this study involves an examination of dyadic interaction. Participants will be paid a maximum of \$100 for completing the laboratory portion of the study. Once at least two members of a friendship group qualify for participation during screening, they are invited back for an experimental laboratory session. Study advertisements allow for friend groups larger than 2 in order to account for ineligible subjects and/or dropout. Two friend dyads are invited to the laboratory for simultaneous beverage administration sessions. On the day of the session, they are randomly assigned to consume alcohol in the company of their own friend, or of the friend of the other participant (an individual with whom they are unacquainted). We adopt this procedure—in which all participants are recruited through a single mechanism—to ensure that the populations of individuals in friend and stranger conditions are comparable and unaffected by selection bias. Within the stranger condition, we will adopt procedures we have used previously to ensure these participants are unacquainted (i.e., all participants are introduced prior to beverage administration and backup participants are invited to all stranger sessions in case the primary 2 participants are previously acquainted).

Dyads will be randomly assigned to receive either a moderate dose of alcohol or a control beverage. The dose will be adjusted for participants' weight and gender and is designed to produce a peak BAC of .08% (0.82-g/kg males; 0.74-g/kg females). Alcoholic beverages will be administered as a soda/juice-vodka cocktail, and control participants will consume an isolvolumic amount of soda/juice. In order to model drinking conditions as they most often manifest outside the laboratory (Senchak et al., 1998), both members of the dyad are assigned to the same beverage condition. We chose not to deceive participants in the control condition about the content of their beverages.

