The ambulatory assessment techniques used in this study were selected for their capability to reliably and unobtrusively measure key constructs of interest. Data from the SCRAM transdermal alcohol monitor will be used to assess alcohol use during the ambulatory assessment period, lasting 14 days. Data from transdermal alcohol monitors will be converted into estimations of BAC using machine learning algorithms developed by our laboratory (Fairbairn et al., 2020). During the ambulatory assessment period, participants will complete self-reports of their mood and take photographs of themselves and their surroundings on their smartphones or, in the event they do not own a smartphone, on one of our lab's iPod touch devices. Participants will complete self-report surveys regarding their mood, their social surroundings, and their alcohol consumption in response to random "pings" or alarms sounding 8 times during their waking hours. Participants will be asked to attend 2 additional (brief) laboratory visits during the ambulatory assessment period—a total of 3 visits, including the original lab orientation session. The first of these visits will take place approximately halfway through the ambulatory assessment period. During this visit, the fit of the transdermal sensors will be assessed, and they will receive feedback on their compliance with ambulatory assessment procedures. At the end of the ambulatory assessment period, participants will review the photographs they took during ambulatory assessment and report their level of acquaintance and relationship quality with each individual depicted therein. During their final visit, they will return the transdermal equipment. Participants will be paid up to \$200 for completion of the ambulatory assessment period.

Statistical Analysis Plan

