Analyses will be conducted using Hierarchical Linear Modeling (HLM; Raudenbush & Bryk, 2002). Models for facial data will involve 3-levels—within-person, between-person, and dyad-level. Raw video frame files—originally recorded for every 1/30th second—will be aggregated into bins for analysis to reflect the duration of facial behaviors as the interaction progresses (Fairbairn et al., 2013; Sayette et al., 2012). Effects of time within the drink period will be entered at level-1 and treated as random at levels 2 and 3. Models for self-reported mood data will involve 2 levels –between-person and dyad-level. Alcohol condition and social familiarity will be entered at the dyad-level as predictor variables. Self-reported positive and negative mood as well as perceived social reinforcement will be each entered at the individual-level as the dependent variables.

Analysis of ambulatory data will also involve HLM, accounting for clustering of observations (level-1) within individuals (level-2). Note that, although ambulatory data will include some complete friendship dyads, we do not anticipate significant clustering at the level of these dyads, although ICC's will be calculated to confirm. An index of BAC and familiarity will be available for each observation, and these variables will be entered at level-1. Follow-up analyses will then parse within-person from between person effects—predictors will be centered according to the individual mean at level-1, and then individual averages will be entered at level-2. Level-1 covariates will include time of day, day of the week, limb of the BAC curve, and physical drinking context and level-2 covariates will include basic demographic variables (gender, age, and personality) (Miranda et al., 2014; Piasecki et al., 2011).

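### Does the ambulatory BAC model need a written rule for limb of the BAC curve at sober prompts?

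*Combined protocol and SAP*

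**What the plan says.** The second paragraph of the Statistical Analysis Plan describes a two-level model, with observations nested in individuals. On the exposures it says "An index of BAC and familiarity will be available for each observation, and these variables will be entered at level-1". Follow-up analyses then separate within-person from between-person effects: "predictors will be centered according to the individual mean at level-1, and then individual averages will be entered at level-2". The next sentence gives the covariates: "Level-1 covariates will include time of day, day of the week, limb of the BAC curve, and physical drinking context". It cites two sources but lists no levels for limb or context.

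The Study Protocol's ambulatory paragraph has random "alarms sounding 8 times during their waking hours", over a period set by this sentence: "Data from the SCRAM transdermal alcohol monitor will be used to assess alcohol use during the ambulatory assessment period, lasting 14 days". Drinking does not trigger the prompts. BAC is itself an estimate: "Data from transdermal alcohol monitors will be converted into estimations of BAC using machine learning algorithms".

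The laboratory part is a separate randomised comparison: "Dyads will be randomly assigned to receive either a moderate dose of alcohol or a control beverage". The official title calls the whole study "A Multimodal Investigation Integrating Laboratory and Ambulatory Methods".

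**The concern.** Limb describes whether BAC is rising or falling. With no BAC curve it has no value, and physical drinking context may have none either. The listed model therefore cannot be fitted to all prompts until somebody adds a coding.

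That coding can matter. If limb is left missing, the sober rows drop out. If it has a separate not-drinking level, the sober-versus-drinking contrast moves from the BAC coefficient to the limb terms. If sober prompts are pooled with one limb, or limb is nested within drinking prompts and set to zero otherwise, most or all of the contrast stays in the BAC coefficient.

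Two analysts could thus report BAC coefficients with different meanings, and only one of these might look like the laboratory alcohol-versus-control result. Because the title speaks of integrating the two methods, that seems a real loss.

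**Working it through.** The plan states no ambulatory sample size, share of prompts while drinking, BAC spread or effect size, so there is no figure of its own to reproduce. From the documents: 8 prompts (read as per day) x 14 days = 112 per person, and a laboratory target peak BAC of .08%. All else is assumed: 100 people, drinking share p = 0.10, drinking BAC with mean m = 0.05 and SD s = 0.03 (CV 0.6), residual SD 1.

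**1. Closed form.** Let the effect be a slope b per unit BAC plus a step d on drinking at all, with sober BAC equal to zero. Over all prompts, Var(BAC) = p s² + p(1-p)m² and Cov(BAC, drinking) = p(1-p)m.

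- Without limb, the BAC coefficient is b + d(1-p)m / [s² + (1-p)m²].
- With a not-drinking limb level, it is b.

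If d = 0 the two agree. If b = 0 and d = 0.5, the first is 0.5 x 0.045 / (0.0009 + 0.00225) = 0.5 x 14.29 = 7.14 and the second is 0.

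The SE grows by sqrt(1 + (1-p)/CV²). This is sqrt(1 + 0.9/0.36) = 1.87 here, 2.63 at p = 0.05 and CV = 0.4, and 1.34 at p = 0.20 and CV = 1.0.

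**2. Mixed-model simulation** (random intercept, ICC 0.4, 40 runs per scenario, same means and shares). BAC coefficient (SE):

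| Limb at sober prompts | Linear, slope 5 | Step 0.5, no slope |
|---|---|---|
| limb omitted | 5.09 (0.545) | 7.06 (0.548) |
| nested, zero when sober | 5.10 (0.546) | 7.09 (0.550) |
| ascending = 1, else 0 | 5.07 (0.610) | 6.01 (0.614) |
| descending = 1, else 0 | 5.06 (0.738) | 5.06 (0.743) |
| three levels | 4.94 (1.003) | -0.05 (1.011) |
| sober rows dropped | 4.94 (1.036) | -0.06 (1.046) |

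**3. A second simulation with other assumptions** (within-person regression, drinking BAC uniform on 0.01 to 0.12, step 0.30, 10% of prompts drinking, 100 runs). Per .08 of BAC, the step-only coefficient is 0.286 without limb, 0.254 with sober prompts pooled with descending, -0.008 with three levels and -0.010 with sober rows dropped. A mixed effect (step 0.15 plus slope 0.15) gives 0.283 pooled and 0.150 with three levels. That is a clear difference, but not an effect against none.

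**4. Where the contrast goes.** Take the step-only case of item 2 and fit a drinking indicator plus BAC, which gives the same BAC coefficient as the three-level limb. The indicator is 0.502 (SE 0.033, with BAC centred at the drinking mean) and the slope is -0.05. The fitted drinking-versus-sober difference at .08 is 0.502 - 0.05 x (0.08 - 0.05) = 0.50, which is the true value. The single coefficient gives 7.06 x 0.08 = 0.56.

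**5. Would a separate drinking term settle it?** Not by itself. With a linear slope of 5, the drinking term is 0.00 if BAC is uncentred, 5 x 0.05 = 0.25 if BAC is centred at the drinking mean, and 5 x 0.08 = 0.40 if centred at .08. Its meaning depends on a further choice, just as the BAC coefficient's does. The fitted difference at .08 is the same throughout: 0.00 + 5 x 0.08 = 0.25 + 5 x 0.03 = 0.40.

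**The case for a change.** The strongest case for a change is that the plan does not fix the meaning of its main ambulatory coefficient, and that a sentence or two would do so. Person-mean centring does not help, because it gives limb no value at sober prompts. The plan nowhere asserts linearity through zero, and the cited sources are not said to supply the coding. Since BAC is estimated, even the division into sober and drinking prompts needs a threshold. Two independent simulations show the same pattern, and the second holds it for 5% to 20% of prompts drinking.

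Much of this stands as description: the coding is unwritten and analysts may differ. Its consequences are narrower.

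- The reversal from a large coefficient to none needs a pure step with no dose response, and also either a three-level limb or dropped sober rows. Dropping about 90% of rows fits poorly with BAC being available for each observation. Under three levels, the contrast appears in the limb terms of the same output.
- The covariate sentence follows the follow-up analyses, so the main BAC model may carry no limb term at all.
- Participants photograph their surroundings, so physical context may be recordable when sober. Limb alone carries the point.
- No passage requires an ambulatory coefficient to match the laboratory contrast. The laboratory comparison is randomised at one target dose. The ambulatory data are observational and may include people recruited from the community.

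**Conclusion.** No change to the plan is needed. The gap is real: limb at sober prompts has no stated coding, and the plan does not say which ambulatory models carry the covariates. But it is a gap that the analyst has to close before the model will run, and the reasonable ways of closing it each estimate a well-defined quantity. If the effect is linear through zero, the choice affects only precision, with an SE factor of 1.34 to 2.63 for a not-drinking level over the ranges examined. If there is also a step at drinking, the choice decides whether that step shows in the BAC coefficient or in the limb terms (0.283 against 0.150 per .08 in the mixed case). Nothing that the plan states is shown to give a wrong result. No single alternative is clearly better: one coefficient blends step and dose, while separate terms lose precision on dose and bring in a centring choice of their own.

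All effect sizes rest on assumed inputs and on simulations that leave out familiarity, time of day and day of the week. The point touches only the additional ambulatory study and leaves the randomised laboratory comparison unaffected.

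### The ambulatory model has no term for mood earlier the same day, so mood that leads to drinking can be counted as alcohol's emotional effect

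*Combined protocol and SAP*

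**What the plan says.** The second paragraph of the Statistical Analysis Plan sets out a two-level model for the ambulatory data, with observations nested in individuals. On exposure it says: "An index of BAC and familiarity will be available for each observation, and these variables will be entered at level-1". On adjustment it says: "Level-1 covariates will include time of day, day of the week, limb of the BAC curve, and physical drinking context". The person-level covariates are gender, age and personality. Follow-up analyses separate within-person from between-person effects: "predictors will be centered according to the individual mean at level-1, and then individual averages will be entered at level-2". The paragraph names no lagged, change-from-earlier, day-level or episode-based term, and it does not name the ambulatory dependent variable.

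The Study Protocol's paragraph on ambulatory assessment says that mood, social surroundings and alcohol consumption are self-reported in response to random "alarms sounding 8 times during their waking hours". The transdermal data are "used to assess alcohol use during the ambulatory assessment period, lasting 14 days", and BAC is derived from them: "Data from transdermal alcohol monitors will be converted into estimations of BAC using machine learning algorithms". Alcohol is randomised in the laboratory part. No assignment of alcohol is described for the ambulatory part.

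**The concern.** The title is about stress and the emotional reward of drinking. That reward is the change in feeling that alcohol brings about. When people decide for themselves when to drink, a hard day or a good day may be the reason for drinking, and the mood of that day may persist into the evening. A model that sets mood at a prompt against BAC at that prompt then mixes two things: what alcohol did to mood, and the mood that was already there.

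The listed covariates describe when, where and with whom the observation was made and where on the BAC curve it fell. The person-level covariates and the person means deal with differences between people. None of these separates one person's good days from the same person's bad days. If low mood leads to drinking, real relief can be hidden. If good mood leads to drinking, reward can be overstated. The ambulatory result could then differ from the randomised laboratory result for reasons that have nothing to do with alcohol or setting.

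**Working it through.** The documents give no sample size, effect size or mood variance for the ambulatory part, so there is no stated figure to reproduce. The check is a derivation followed by simulation on assumed inputs.

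**1. Where the bias comes from.** Write mood for person i, day j, prompt t as

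mood = u_i + d_ij + β·BAC_ijt + error,

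where u_i is the person's usual level and d_ij is that day's departure from it. Centring BAC on the person mean removes u_i but leaves d_ij. The within-person coefficient then tends to

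β + Cov(d, BAC*) / Var(BAC*),

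where BAC* is within-person BAC after adjustment for the other covariates. The second term is zero if day mood does not influence drinking. Otherwise it takes the sign of that influence.

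**2. Day-level mood (all inputs assumed except 14 days and 8 prompts, the latter read as per day).** 150 people; total mood SD about 1; true effect β = 0.20 SD; drinking only at the last two prompts; adjustment for time slot and weekday only, so familiarity, physical context and limb are left out; 25 replicates per scenario. The odds ratios for drinking per SD of day mood are exp(−0.5) = 0.61, exp(−0.25) = 0.78, 1, exp(0.25) = 1.28 and exp(0.5) = 1.65. The adjusted model adds the mean of earlier zero-BAC mood ratings that day, with a slope that varies by time slot. Share of bias removed = 1 − |adjusted − 0.20| / |concurrent − 0.20|.

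| Odds ratio | Day-mood SD | Concurrent | Adjusted | Bias removed |
|---|---|---|---|---|
| 0.61 | 0.3 | 0.086 | 0.136 | 1 − 0.064/0.114 = 44% |
| 0.61 | 0.5 | 0.002 | 0.139 | 1 − 0.061/0.198 = 69% |
| 0.78 | 0.3 | 0.137 | 0.160 | 1 − 0.040/0.063 = 37% |
| 0.78 | 0.5 | 0.090 | 0.160 | 1 − 0.040/0.110 = 64% |
| 1 | 0.3 | 0.201 | 0.203 | no bias |
| 1 | 0.5 | 0.202 | 0.207 | no bias |
| 1.28 | 0.3 | 0.267 | 0.240 | 1 − 0.040/0.067 = 40% |
| 1.28 | 0.5 | 0.306 | 0.241 | 1 − 0.041/0.106 = 61% |
| 1.65 | 0.3 | 0.330 | 0.282 | 1 − 0.082/0.130 = 37% |
| 1.65 | 0.5 | 0.419 | 0.280 | 1 − 0.080/0.219 = 63% |

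Repeats on similarly assumed inputs agreed. When low mood led to drinking, the concurrent estimate was about −0.02 to 0.08 and the adjusted one 0.12 to 0.14. When good mood did, they were 0.33 to 0.43 and 0.25 to 0.27. With no link, both were about 0.20.

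**3. Mood carried from prompt to prompt (all inputs assumed except 14 days and 8 prompts).** 400 people; within-day autocorrelation ρ of 0.3, 0.5 or 0.7; one drinking opportunity at prompt 6; log-odds of drinking per SD of mood at prompt 5 of 0, 0.3 or 0.6. With a true effect of zero and a positive link, the person-centred concurrent estimate was 0.04 to 0.06 (ρ = 0.3), 0.11 to 0.17 (ρ = 0.5) and 0.15 to 0.31 (ρ = 0.7). Adjusting for the prompt-5 rating gave −0.004 to 0.010. With no link, both models were within about 0.03 of zero. Each scenario is a single run.

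**4. Cost in observations.** 14 × 8 = 112 prompts per person if all are answered. The first prompt of each day has no earlier rating: 14/112 = 1 in 8, which leaves at most 98.

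**The case against.** The strongest reply is that the documents do not show the bias occurring. Nothing in them says that mood drives drinking in this sample, or in which direction. The second paragraph of the Statistical Analysis Plan does not name mood as the ambulatory outcome and does not call the BAC coefficient an effect of alcohol. The same-prompt pairing is read from BAC being attached to each observation, and a covariate list that says what it will include need not be complete. All of this stands, and it makes the point conditional. It does not supply the missing term.

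Three stronger readings are tempting and not supported:

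- A reader might infer that prior mood is counted as alcohol's effect as a matter of course. The rows with an odds ratio of 1 show no bias, so the most that can be said is that it can be.
- A reader might infer that the pre-drinking ratings are discarded. They are not. Prompts at zero BAC are observations in the planned model and form part of its sober comparison. What is absent is their use as a covariate for later prompts on the same day.
- A reader might take 0.0 to 0.4 as the error of the planned model. The planned model also contains familiarity, physical context and limb, which the simulation leaves out. Company in particular may track celebratory drinking and absorb some of the bias.

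It is also fair to say that the near-complete correction in the third step of the check follows almost by construction, because the rating adjusted for is the one that triggers drinking. The partial correction in the second step is the better guide. Finally, the ambulatory part stays observational with or without the added covariate.

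**Conclusion.** The point holds in conditional form. For self-chosen drinking, the ambulatory model has no term for how the person felt earlier that day. If the outcome is mood at the same prompt, and if mood influences drinking and persists through the day, the BAC coefficient mixes prior mood with alcohol's effect, and person-mean centring does not separate them. On assumed inputs a true 0.20 SD came out between about 0.0 and 0.4. Those figures show that the bias can be as large as the effect itself. They do not predict its size or sign in this study. Adding earlier same-day mood removed 37% to 69% of the bias in the day-level scenarios and changed almost nothing when there was no link. The randomised laboratory comparison of alcohol with the control beverage is not touched.

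**What to change.** Name the ambulatory outcome and state that it is paired with BAC at the same prompt, if that is the intention. Then add a prespecified ambulatory model with one further level-1 covariate: the average of the same mood scale over that day's prompts before the first positive estimated BAC, always earlier than the prompt being modelled. On days without drinking this is simply the prompts earlier than the current one. Centre it on the person mean and let its slope vary by time of day. Stopping at the first positive BAC keeps out ratings made after an earlier drinking episode the same day. Define the day so that drinking past midnight stays with the day on which it began.

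Report this model beside the planned concurrent model. Base any statement about alcohol's emotional effect on the adjusted model, and describe the concurrent coefficient as an association.

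The cost is one derived variable from data already being collected. Prompts with no earlier pre-drinking rating that day drop out: at least 1 in 8, and more with missed prompts or when the first answered prompt already shows alcohol. The adjustment reduces the confounding but does not remove it, because earlier ratings are a noisy measure of the day's mood, and the report should say so.
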